3.9 Safety Analysis

Safety analyses will be conducted using the safety analysis set.

3.9.1 Adverse Events

All adverse events will be coded using the MedDRA Version 17.0 and will be classified by MedDRA SOC and PT. Analyses of adverse events will be performed using the safety analysis set.

AEs that started on or after the first dose of study medication or worsened after the first dose of study medication are considered treatment-emergent AEs (TEAEs). TEAEs will be assigned to the run-in period or the double-blind period in the same manner. TEAEs occurring during the run-in period will be listed only.

For all summaries, SOCs and PTs within SOC will be presented by decreasing frequency of incidence for all active treatment groups combined.

Handling of Missing or Partial Start Dates for Adverse Events

Rules for handling incomplete or missing adverse event start dates are addressed below (stop dates will not be imputed). Once implemented, the adverse event start date will be used to identify treatment-emergent adverse events for both run-in and double-blind treatment periods.

In the unusual case that the month portion of an adverse event start date is missing but the day portion is not missing, the day portion will be assumed to be missing.

Likewise, in the case where the year portion of an adverse event start date is missing but the month and/or day portion is not missing, the month and/or day portion will be assumed to be missing. All missing portion(s) of the date will be handled using the same rules:

- In the event that the day portion (and only the day portion) of the date is missing:
 - If the adverse event started in the same month and year as the first dose date, the adverse event start date will be assumed to be the first dose date.
 - Otherwise, the adverse event start date will be assumed to be the last day of the given month and year, e.g., XX–DEC-2005 would be 31-DEC-2005 where XX represents an unknown day.
- In the event that the day and month portions (and only the day and month portions) of the date are missing:
 - If the adverse event started in the same year as the first dose date, the adverse event start date will be assumed to be the first dose date.
 - Otherwise, the adverse event start date will be assumed to be last month and day of the given year, e.g., XX–XXX-2005 would be 31-DEC-2005 where XX represents an unknown day and XXX represents an unknown month.
- In the event that the day, month, and year portions of the adverse event start date are missing, it will be assumed to be the first dose date.
- If the adverse event start date has been imputed using the rules above, then the adverse event start date must be compared with the adverse event stop date to ensure the logical ordering of dates. If the imputed adverse event start date is after the non-missing adverse event stop date, then the imputed start date will be reset as the stop date.

3.9.1.1 Overall Summary of AEs

An overall summary of TEAEs will be presented by treatment group and for all active treatment groups combined. The number and percentage of subjects who experienced

at least one TEAE, at least one severe TEAE, at least one treatment-related TEAE, at least one serious TEAE, at least one treatment-related serious TEAE, at least one TEAE leading to study drug discontinuation, at least one TEAE leading to study withdrawal and at least one TEAE leading to death will be displayed. Treatment-related TEAEs are events with a study drug causality of ‘possible’, ‘probable’ or ‘definite.’

3.9.1.2 AE Incidences

The incidence of TEAEs will be presented by treatment group and for all active treatment groups combined. The number and percentage of subjects who experienced at least one TEAE as well as the number and percentage of subjects who experienced each specific SOC and PT will be presented. For this analysis, if a subject has more than one occurrence of the same PT, then the PT will be counted only once for that subject. Similarly, if a subject has more than one occurrence of the same PT within a SOC, the subject will be counted only once in that SOC.

A summary table by PT will be presented using the same methods as described above for the by SOC and PT summary table.

All TEAEs will be included in a subject listing.

3.9.1.3 Maximum Severity

The incidence of TEAEs will be presented by maximum severity and by treatment group and for all active treatment groups combined. For this analysis, if a subject experiences more than one occurrence of the same PT, the subject will be counted only once under the maximum severity at which it was experienced (mild, moderate, severe). TEAEs with missing severity will be counted as severe.

3.9.1.4 Related AEs

The incidence of drug-related TEAEs will be presented by treatment group and for all active treatment groups combined. Related TEAEs are those with a ‘possible’, ‘probable’ or ‘definite’ relationship to treatment. TEAEs with missing relationship will be counted as related. For this analysis, if a subject has more than one occurrence of the same PT, then the PT will be counted only once for that subject. Similarly, if a subject has more than one occurrence of the same PT within a SOC, the subject will be counted only once in that SOC.

3.9.1.5 Deaths, Serious AEs and AEs That Led to Discontinuation

Subject data listings of fatal AEs, serious AEs, AEs that led to treatment discontinuation and AEs that led to study withdrawal will be presented.

3.9.1.6 AEs of Special Interest

Adverse events of special interest include the following categories:

- Genital mycotic infections
- Urinary tract infections including urosepsis and pyelonephritis
- Diuretic effects including hypovolemia
- Hypotension episodes
- Hepatotoxicity
- Major Adverse Cardiovascular Event (MACE)
- Hypoglycemia
- Falls and fractures
- Malignancies
- Hypersensitivity reactions
- Acid-base disorders
- Renal failure events

All AEs of special interest will be identified by appropriate MedDRA preferred term during a blinded review of the data.

The incidence of TEAEs of special interest by treatment group and for all active treatment groups combined will be presented separately for each category. The number and percentage of subjects who experienced at least one TEAE of special interest as well as the number and percentage of subjects who experienced each specific SOC and PT will be presented. For this analysis, if a subject has more than one occurrence of the same PT, then the PT will be counted only once for that subject. Similarly, if a subject has more than one occurrence of the same PT within a SOC, the subject will be counted only once in that SOC.

3.9.1.7 Hypoglycemia Events

Hypoglycemic event categories include:

Category	Description
Severe	Assistance required and blood glucose ≤ 70 mg/dL or no value available but responded to glucose treatment
Documented Symptomatic	Blood glucose ≤ 70 mg/dL and typical symptoms of hypoglycemia
Asymptomatic	Blood glucose ≤ 70 mg/dL and no typical symptoms of hypoglycemia
Probable Symptomatic	Typical symptoms of hypoglycemia and no value available but responded to glucose treatment
Relative	Typical symptoms of hypoglycemia and blood glucose > 70 mg/dL

While each event meeting the criteria above will be entered into the hypoglycemia log, only critical (severe) hypoglycemia, documented symptomatic hypoglycemia, asymptomatic hypoglycemia, and probable hypoglycemia will be entered as AEs.

Subjects will be dichotomized into two categories, having a hypoglycemic event during the double-blind period (i.e., meeting one of the above categories) or not having a hypoglycemic event during the double-blind period. The number and percentage of subjects in each category will be summarized by treatment group for the safety analysis set. For this analysis, if a subject experiences more than one occurrence of a hypoglycemic event, the subject will be counted only once under the maximum severity at which it was experienced ('relative', 'probable symptomatic', 'asymptomatic', 'documented symptomatic', 'severe'). A logistic model will be used to characterize treatment differences in the proportions of subjects with at least one hypoglycemic event. For this model, the dependent variable will take values of 1='Event' or 0='No Event' and the predictor variables will include treatment, study center, baseline FPG and prior anti-diabetic treatment status. Odds ratio for the treatment difference versus placebo, its 95% confidence interval and the associated p-value will be presented.

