1. Severe hypoglycemia: an event requiring assistance by another person to actively administer carbohydrate, glucagon, or other resuscitative actions. These episodes may be associated with sufficient neuroglycopenia to induce seizure or coma. Plasma glucose measurements may not be available during such an event, but neurological recovery attributable to the restoration of plasma glucose to normal is considered sufficient evidence that the event was induced by a low plasma glucose concentration. All such events should be recorded as serious adverse events in the CRF.
2. Documented symptomatic hypoglycemia: an event during which typical symptoms of hypoglycemia are accompanied by a measured plasma glucose concentration ≤ 70 mg/dL (3.9 mmol/L).
3. Asymptomatic hypoglycemia: an event not accompanied by typical symptoms of hypoglycemia but with a measured blood glucose concentration ≤ 70 mg/dL (3.9 mmol/L).
4. Probable symptomatic hypoglycemia: an event during which symptoms of hypoglycemia are not accompanied by a blood glucose determination but that is presumably caused by a blood glucose concentration ≤ 70 mg/dL (3.9 mmol/L).

5. Relative hypoglycemia: An event during which the person with diabetes reports any of the typical symptoms of hypoglycemia, and interprets those as indicative of hypoglycemia, but with a measured plasma glucose concentration > 70 mg/dL (3.9 mmol/L).

While each event meeting the criteria above will be entered into the hypoglycemia log, only critical hypoglycemia, documented symptomatic hypoglycemia, asymptomatic hypoglycemia, and probable hypoglycemia will be entered as AEs.

In the event of asymptomatic hypoglycemia, the investigator should review the signs and symptoms of hypoglycemia with the subject to elicit a complete description and should review proper glucometer technique to ensure that the low glucose value is not due to improper use of the glucometer.

The investigator should be alert to the likelihood of improper glucose measurement technique if a study subject reports an SMBG value < 55 mg/dL that is not associated with any signs or symptoms of hypoglycemia and is not treated by some form of glucose administration.

In the event of probable symptomatic hypoglycemia, the investigator should encourage the subject to obtain glucose values, when possible, in the context of signs and symptoms of hypoglycemia, even if the glucose value is measured after treatment for the symptoms is administered.

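### SAP 3.9.1.7 defines severe and probable symptomatic hypoglycemia more narrowly than protocol 6.10.9, so some protocol-defined events drop to relative or meet no category (minor)

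*SAP*

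**What the plan says.** Both documents list five hypoglycemia categories under the same names, and both enter all but the relative category as adverse events.

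- **Severe, protocol 6.10.9:** "an event requiring assistance by another person to actively administer carbohydrate, glucagon, or other resuscitative actions". No glucose threshold is attached. The text adds that a glucose measurement may be unavailable and that "neurological recovery attributable to the restoration of plasma glucose to normal is considered sufficient evidence" of a low glucose cause. It then says: "All such events should be recorded as serious adverse events in the CRF".
- **Severe, SAP 3.9.1.7:** "Assistance required and blood glucose ≤ 70 mg/dL or no value available but responded to glucose treatment".
- **Probable symptomatic, protocol 6.10.9:** an event in which "symptoms of hypoglycemia are not accompanied by a blood glucose determination but that is presumably caused by a blood glucose concentration" at or below 70 mg/dL. Treatment and response are not mentioned.
- **Probable symptomatic, SAP 3.9.1.7:** "Typical symptoms of hypoglycemia and no value available but responded to glucose treatment".

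The SAP then splits subjects into those with an event meeting one of its five rows and those without. It tabulates each subject once under the most severe category, with relative ranked lowest and severe highest, and fits a logistic model to the event/no-event outcome. The output is Table 14.3.3. The SAP does not say that its rows depart from the protocol.

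**The concern.** Investigators record events under the protocol wording, while the table is specified under the SAP wording. Where the SAP row is narrower, an event that the protocol counts can lose its category or move to the lowest one. Table 14.3.3 is the only planned table of hypoglycemia by category, and hypoglycemia is an adverse event of special interest. If the SAP rows are applied literally, the table could show no severe event while the serious adverse event listing shows one. It could also score as event-free a subject who has a hypoglycemia AE on record.

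**Working it through.** No stated figure in the plan bears on this point, so the check is a cross-walk of the two sets of definitions.

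**Inputs.** The protocol rows come from protocol 6.10.9 and the SAP rows from SAP 3.9.1.7. The SAP severe row is read as assistance AND (glucose ≤70 mg/dL OR no value with response to glucose). An event that needs assistance is taken as severe under the protocol, because the protocol makes all such events SAEs. An unmeasured symptomatic event is taken as probable where the investigator presumes a low glucose.

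**Two readings of the SAP's glucose value.** The protocol diary collects a reading at the time of symptoms and a separate reading 15 minutes after carbohydrate. The SAP does not say which one classifies an event. The rows were therefore applied twice: once counting any recorded value, and once counting only an event-time value.

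| Event | Protocol | SAP, any value | SAP, event-time value only |
|---|---|---|---|
| 1. Unassisted, symptoms, no glucose, untreated | Probable (AE) | No row | No row |
| 2. Unassisted, symptoms, no glucose, treated, no response | Probable (AE) | No row | No row |
| 3. Assisted, symptoms, event-time glucose >70 | Severe (SAE) | Relative | Relative |
| 4. Assisted, no typical symptoms recorded, event-time glucose >70 | Severe (SAE) | No row | No row |
| 5. Assisted, no glucose, no response | Severe (SAE) | No row | No row |
| 6. Assisted, symptoms, only a post-treatment glucose >70, responded | Severe (SAE) | Relative | Severe |
| 7. Assisted, only a post-treatment glucose ≤70, responded | Severe (SAE) | Severe | Severe |

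**What follows for Table 14.3.3.**

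- Cases 1, 2, 4 and 5 meet no SAP row under either reading. A subject with only such an event is scored 0 in the dichotomy and the logistic model.
- Case 3 moves from the highest category to the lowest under either reading. Relative still counts as an event, so the subject stays at 1 and the any-event odds ratio does not change. Only the category tabulation does.
- Case 6 moves only if the post-treatment reading is taken as the event's glucose. Case 7 does not move.

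**Size.** With about 80 subjects per arm, one reclassified subject is 1/80 = 1.25% of the arm. This is the weight of a single subject and does not estimate how often the shift would occur. The documents give no event rate, and protocol 3.3 expects minimal hypoglycemia risk.

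**The case against.** **The SAP row can be read as an operational form of the protocol.** Protocol 6.10 defines hypoglycemia by a value at or below 70 mg/dL, and the recovery sentence in 6.10.9 ties a severe event without a measurement to low glucose. This explains the likely intent, but it does not remove the mismatch. The protocol calls recovery sufficient evidence, not a requirement, and attaches no glucose condition to its instruction to record all such events as SAEs. Nor does this argument reach the probable symptomatic row.

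**The log category may be what is tabulated.** Protocol 6.10.9 has events recorded in a hypoglycemia log under its five categories, and the SAP does not say that categories are derived from raw data. If the category assigned under the protocol is used, none of the shifts occurs. This stands as a condition on the point. The SAP does not say that the log category is used, and it presents its own rows as the criteria for log entry, so the two texts still need reconciling.

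**The events are not lost.** AE and SAE entry follows the protocol. A severe event would still appear in the serious-event row of Table 14.3.1.1, in Table 14.3.1.3, in the special-interest summary in Table 14.3.2, and in Listings 16.2.7.2 and 16.2.16. This stands, and it limits the consequence to disagreement between outputs.

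**A stronger reading that fails.** A reader might infer that any assisted event measured only after treatment falls to relative. Cases 6 and 7 show otherwise: the value must exceed 70 mg/dL, it must be taken as the event's glucose, and typical symptoms must be present. If such a reading is treated as leaving no value available, a responder stays severe. Nor does the protocol's encouragement to obtain a value "even if the glucose value is measured after treatment for the symptoms is administered" show that such readings are likely in assisted events, because that sentence concerns probable symptomatic events. The protocol's own relative category also gives no timing for its glucose value, so for unassisted events that ambiguity did not start with the SAP.

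**Conclusion.** The two documents conflict on two of the five categories, and the SAP does not acknowledge it. The firm part is that cases 1 to 5 differ under either reading of the glucose value, provided the SAP rows are applied to the data. The omission from the probable symptomatic row matters more for inference, because it can turn a protocol-defined AE into a no-event outcome in the logistic model. The move from severe to relative affects only the category tabulation.

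A reader might also infer that hypoglycemia would be understated mainly in the active arms, or that dose selection is at risk. The documents support neither. They give no rate by arm, the stated basis for choosing doses is HbA1c change, and no dose rule uses Table 14.3.3. The issue is a minor inconsistency in one safety table, of unknown frequency.

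**What to change.** In SAP 3.9.1.7:

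1. Use the protocol 6.10.9 definitions for the severe and probable symptomatic rows, so that every protocol-defined hypoglycemia AE counts as an event and Table 14.3.3 agrees with the AE and SAE records.
2. State which glucose reading, event-time or post-treatment, classifies an event.
3. State whether the category is taken from the hypoglycemia log or derived from the recorded data.

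This concerns classification for analysis only and proposes no new clinical threshold. A rule that a reading taken after carbohydrate can never place an event in the relative category is in neither document and is not needed; item 2 closes that gap.

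The cost is SAP wording and, if the category is derived, one programmed flag settled before database lock. The protocol diary already collects assistance, both glucose readings and resolution, and the supplemental CRF takes in the diary data. The downside is small: a few events of uncertain glucose cause would stay in the severe and probable rows.

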Hypoglycemia is defined as any FPG or SMBG value ≤ 70 mg/dL and documented as described in [Section 6.10.9](#).

Any increase in liver function tests (AST, ALT, or bilirubin) greater than 3 times the ULN for the laboratory utilized will be considered a clinical laboratory adverse event.

Severity: Adverse events will be graded on a 3-point scale and reported as indicated on the CRF. The intensity of an adverse experience is defined as follows:

1 = Mild: discomfort noticed, but no disruption to daily activity;

2 = Moderate: discomfort sufficient to reduce or affect normal daily activity;

3 = Severe: inability to work or perform normal daily activity.

Investigational Product Causality: An assignment made by the investigator based on the circumstances of the event and its analysis. Cases with causal relationship classified as possible, probable or definite are defined as related. Cases with causal relationship categorized as not likely or unrelated are defined as not related. Relationship of an adverse event to dosing will be assessed as follows:

Definite: The event responds to withdrawal of the investigational product (dechallenge), and recurs with rechallenge by administration of the investigational product.

Probable: There is a reasonable causal relationship between the investigational product and the AE. The event responds to dechallenge. Rechallenge is not required.

Possible: There is a reasonable causal relationship between the investigational product and the AE. Dechallenge is lacking or unclear.

Not Likely: There is a temporal relationship to investigational product administration, but there is not a reasonable causal relationship between the investigational product and the event.

Unrelated: There is not a temporal or causal relationship to investigational product administration.

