6.10.9 Hypoglycemia

Events of hypoglycemia or potentially representing hypoglycemia should be carefully evaluated.

All subjects will be provided with a glucometer and diary for recording blood glucose measurements and signs and symptoms of hypoglycemia. During the study the subject is expected to record daily SMBG readings and all signs and symptoms that may potentially reflect hypoglycemia. In the event of such signs or symptoms, the subject is expected to check the blood glucose if it is reasonably safe to do so, and consume carbohydrates, if appropriate, to treat hypoglycemia.

The subject will be expected to record in the glycemic control diary the following information for each hypoglycemic event:

1. Signs and symptoms attributed to hypoglycemia and the time and date on which they occurred
2. SMBG reading at the time of the signs and symptoms attributed to hypoglycemia
3. Time elapsed from the most recent meal to the onset of signs and symptoms
4. Duration, intensity, and type of any exercise within the 24 h prior to the signs and symptoms
5. Type of treatment used (e.g., juice, crackers) for the signs and symptoms and whether assistance was required from another person to administer the treatment
6. SMBG reading 15 minutes after treatment with carbohydrate and the time at which this was measured
7. Whether or not the signs and symptoms attributed to hypoglycemia resolved after blood glucose returned to normal.

Subjects are encouraged to call the study clinic should signs and symptoms potentially related to hypoglycemia occur.

At each study visit, the investigator is expected to review the glucometer and glycemic control diary with particular attention to any SMBG value ≤ 70 mg/dL and any recorded signs or symptoms potentially related hypoglycemia. In addition, the investigator should query the subject with regard to the occurrence of signs and symptoms potentially related to hypoglycemia even if none are recorded in the diary.

In the event of a blood glucose value ≤ 70 mg/dL or signs and symptoms potentially related to hypoglycemia, the investigator should complete the supplemental CRF which will include data from the glycemic control diary and action items to reduce future hypoglycemia episodes.

Hypoglycemia events will be recorded in the hypoglycemia log under 5 categories:

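### The only hypoglycemia model in the SAP counts 'relative' events (measured glucose above 70 mg/dL); adding an adjusted odds ratio for the four categories entered as AEs would be a cheap improvement

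*SAP*

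**What the plan says.** SAP 3.9.1.7 lists five categories: severe, documented symptomatic, asymptomatic, probable symptomatic and relative. It describes the last as "Typical symptoms of hypoglycemia and blood glucose > 70 mg/dL". The binary outcome is "having a hypoglycemic event during the double-blind period (i.e., meeting one of the above categories"). For the accompanying summary, "the subject will be counted only once under the maximum severity at which it was experienced", and the severity order for that summary names 'relative' as its lowest level. The logistic model adjusts for study center, baseline FPG and prior anti-diabetic treatment. It yields an odds ratio against placebo with a 95% CI and p-value, reported in Table 14.3.3.

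Protocol 6.10 states "Hypoglycemia is defined as any FPG or SMBG value ≤ 70 mg/dL". Protocol 6.10.9 states "Hypoglycemia events will be recorded in the hypoglycemia log under 5 categories", and then that "only critical hypoglycemia, documented symptomatic hypoglycemia, asymptomatic hypoglycemia, and probable hypoglycemia will be entered as AEs". SAP 3.9.1.7 repeats that restriction. Hypoglycemia reported as an AE is otherwise summarised only as numbers and percentages, in the AE tables and in the special-interest table (SAP 3.9.1.6, Table 14.3.2). Protocol 9.6 plans no hypoglycemia model.

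**The concern.** This is the only safety endpoint in the SAP with a planned odds ratio and p-value. It sits under the adverse-event heading, so a reader may take it as the adjusted comparison for the hypoglycemia reported as AEs. It is not. It also counts subjects whose only event was symptoms with a reading above 70 mg/dL.

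Protocol 3.3 expects the risk of induced hypoglycemia to be minimal. If AE-qualifying events are rare, a few relative-only subjects can be a large share of the modelled events. When those subjects are equally common in every arm, the odds ratio moves toward 1, which in a safety comparison makes an excess look smaller. The adjusted four-category estimate, its interval and its p-value cannot be rebuilt from any planned output.

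**Working it through.** **Which events are modelled.** The phrase about the above categories could be read as pointing only to the four AE categories in the sentence before it. The severity order for the same analysis includes 'relative', so that reading fails and the model has five categories.

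**What can be recovered.** Each subject is counted once at the worst category, and 'relative' ranks lowest. A subject shown under 'relative' therefore had nothing else, and the other four rows of Table 14.3.3 sum to the crude four-category count. The adjusted estimate does not follow from those counts.

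**Size.** The documents give neither hypoglycemia rates nor a power figure for this model, so there is no plan figure to reproduce and every rate below is an assumption. The 80 per arm is from SAP 2.2.1. Odds ratios are crude.

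Let p be the four-category rate and r the relative-only rate among the remaining subjects. The five-category rate is q = p + (1 − p)r, and OR = [q1/(1 − q1)] / [q0/(1 − q0)]. Example: p = 2% and 4% with r = 2% in both arms gives q0 = 0.02 + 0.98 × 0.02 = 0.0396 and q1 = 0.04 + 0.96 × 0.02 = 0.0592, so OR = 1.53.

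| Relative-only, placebo / active | OR, four-category 2% vs 4% | OR, four-category 2% vs 6% |
|---|---|---|
| not counted | 2.04 | 3.13 |
| 2% / 2% | 1.53 | 2.07 |
| 4% / 4% | 1.35 | 1.72 |
| 4% / 2% | 1.00 | 1.36 |
| 2% / 4% | 2.06 | 2.62 |
| 2% / 6% | 2.62 | 3.19 |

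The Woolf 95% interval at expected counts is exp(ln OR ± 1.96 √Σ(1/expected cell)). For the four-category odds ratios it is 0.30 to 13.98 (OR 2.04) and 0.51 to 19.25 (OR 3.13). Every other value in each column lies inside. Power at two-sided 5% (exact enumeration, uncorrected chi-square) is 10% for four categories against 7% for five in the first column, and 22% against 14% to 16% in the second, with equal relative-only rates of 2% or 4%.

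**Sparsity**, at 2% vs 4% with 2% relative-only in each arm:
- Expected events in 320 subjects: 80 × 0.02 + 240 × 0.04 = 11.2 for four categories; 80 × 0.0396 + 240 × 0.0592 = 17.4 for five.
- Placebo arm with no events: 0.98^80 = 0.20 against 0.9604^80 = 0.04.
- At least one of four arms with no events: 1 − (1 − 0.199)(1 − 0.038)^3 = 0.29 against 0.06.
- Centers: the cap of 32 per site implies at least 320/32 = 10 centers. Assume 10 equal centers with 8 subjects per arm. A given center has no events with probability 0.98^8 × 0.96^24 = 0.319, so at least one of ten does with probability 1 − (1 − 0.319)^10 = 0.98. The five-category figure is 1 − (1 − 0.167)^10 = 0.84, where 0.9604^8 × 0.9408^24 = 0.167. In about 69% of simulated four-category trials a center was empty while no arm was. A fallback triggered only by an empty arm would miss those.

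**The case against.** The strongest reply is that nothing here is an error. SAP 3.3.3 lists the percentage of subjects with a hypoglycemic event as a safety variable separate from AE incidence, and the model follows it with a stated outcome. Protocol 6.10.9 itself calls all five categories hypoglycemia events, and the Protocol 6.10 definition refers to that section for documentation. The Protocol Synopsis describes safety as assessed descriptively, no AE category is promised an adjusted odds ratio, and Table 14.3.3 shows the 'relative' row beside the model. All of this stands. A reader might infer that the SAP contradicts itself or leaves AE hypoglycemia unanalysed. The documents do not support that: the endpoint is explicit, and crude incidence of AE hypoglycemia is planned.

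The threshold argument also has limits. Probable events, and some severe ones, have no glucose value, so the four-category outcome follows the AE-entry list and not the literal 70 mg/dL definition. Protocol 6.10.9 encourages readings "even if the glucose value is measured after treatment for the symptoms is administered", so some relative events may have been at or below 70 mg/dL at onset. If half of the relative-only subjects (2% in each arm) were, the odds ratio for true plus recorded events would be 1.70 (2% vs 4%) or 2.43 (2% vs 6%), between the five- and four-category values. Neither definition is plainly the right one, which argues for reporting both and not for replacing the current model.

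Finally, the illustration compares crude odds ratios, while the missing item is an adjusted one. That is fair: the table shows how far the target can shift, not what adjustment would add.

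**Conclusion.** The point holds as a cheap improvement, not as a defect. The single planned odds ratio answers a question about any logged event. No adjusted estimate is planned for the four categories entered as AEs, and none can be derived from the planned tables.

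A reader might go further and infer that the plan hides a hypoglycemia signal. The documents do not support that either. The pull toward 1 needs similar relative-only rates across arms; with different rates the odds ratio can rise, fall or stay put (with four-category rates of 2% and 4% and 2% relative-only on placebo, there is no shift at 3.92% on active). On the assumed rates every shift is well inside the sampling error, power is low under either definition, and no decision rule uses the p-value. What is at stake is interpretation. The textual part is certain; the size rests wholly on assumed rates.

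**What to change.** In SAP 3.9.1.7, keep the current model and label it 'any logged event (including relative)'. Beside it, fit the same model with Event = 1 for severe, documented symptomatic, asymptomatic or probable symptomatic events. Report both in Table 14.3.3 and keep the 'relative' row.

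Prespecify a penalised (Firth) fit for both models, or at least whenever any arm or any (pooled) center has no events; an empty arm alone is too narrow a trigger.

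Add a footnote that the four-category count need not match the hypoglycemia entry in Table 14.3.2, since "All AEs of special interest will be identified by appropriate MedDRA preferred term during a blinded review of the data".

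The cost is a few sentences and one derivation on data already collected, and nothing planned is lost. The downside is a sparser second model: about 11 expected events against 17 in 320 subjects at the assumed rates, with a wider interval.
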